1.4 Hypothesis

Subjects treated with nivolumab will have an overall improved response to liver directed therapy with Y-90 (Therasphere) as evidenced by markers of angiogenesis, radiographic response defined by RECIST criteria, immunological markers; leading to improved clinical outcome measurements, less recurrence and potentially meet criteria for liver transplantation.

1.5 Exploratory Studies

It has been shown in animal models, control human subjects as well as in oncology patients that, administration of nivolumab modifies the cytokine levels in plasma.

1.5.1 Exploration of the correlation between PD-1, PD-L1 and PD-L2 expression and CD4+ and CD8+ tumor infiltrating lymphocytes and PFS, OS and response to treatment.

PD-1 is a key immune checkpoint receptor expressed by activated T cells and mediates immunosuppression. PD-1 functions primarily in peripheral tissues, where T cells may encounter the immunosuppressive PD-1 ligands PD-L1 and PDL-2, which are expressed by tumor cells, stromal cells or both [1-3]. PD-L1 and PD-L2 are overexpressed in a variety of solid tumors however no data exists in ACC [1].

There are conflicting data on the predictive value of PD-L1 expression on PD-1 directed therapy in solid tumors [1, 4]. Herbst et al showed that patients with solid tumors including non-small cell lung cancer and melanoma treated with humanized PD-L1 antibody had higher ORR when immunohistochemistry showed intense staining for PD-L1 in the tumor [5]. The same correlation was not observed on stratified analysis according to tumor cell membrane PD-L1 expression of non-small cell lung cancer patients treated with nivolumab therapy in the second line setting [4].

Pathological slides from tumor archival tissue will be stained using a monoclonal antibody against PD-L1 and defined as PD-L1 positive if equal or greater than 5% of the tumor cells membrane analyzed. We hypothesize that tumor cell membrane expression of PD-L1 or PD-L2 can have an impact on treatment responses.

1.5.2 Peripheral blood lymphocyte phenotypes

Lymphocyte subsets (CD3, CD4, CD8, CD19, and CD56) will be analyzed according to absolute cell numbers per microliter of whole blood, percent representation among all lymphocytes, and co-expression of the activation markers CD25, HLA-DR, and CD45RO using automated flow cytometric techniques at the Flow Cytometry Core Laboratory, Robert H Lurie Cancer Center of Northwestern University under the supervision of [name].

- 1.5.3 Measurement of humoral and cellular responses to tumor antigens on serum samples by measuring the levels of cytokines (i.e., IL-2, IL-6, IL-8, IL-10, IL-18, IFN γ and TNF- α) and peripheral blood lymphocyte phenotype.**
Measures of immunologic response correlate with lack or presence of response to treatment with nivolumab.

2.0 OBJECTIVES & ENDPOINTS

2.1 Primary Objectives & Endpoints

- 2.1.1 Phase I:** To identify maximum tolerated dose (MTD) of nivolumab for combination treatment of nivolumab and Y-90 in patients with advanced hepatocellular carcinoma. The MTD will be defined as the highest dose that causes dose limiting toxicities (DLTs) in <2 of 6 patients.
- 2.1.2 Phase Ib:** To evaluate the proportion of patients with objective response rate (ORR, according to RECIST criteria version 1.1) to the combination treatment of nivolumab with Y-90.

2.2 Secondary Objectives & Endpoints

- 2.2.1** To evaluate the proportion of patients alive and progression free at 24 weeks in the described population.
- 2.2.2** To evaluate the toxicities (according to the NCCN CTCAE v4.03) and tolerability of nivolumab and y-90 in patients with advanced hepatocellular carcinoma
- 2.2.3** To determine the disease control rate (DCR) to the combination of nivolumab and Y-90 at 24 months from the start of nivolumab treatment. DCR is defined as the sum of Complete Response, Partial Response, and Stable Disease (DCR = CR + PR + SD).

2.3 Exploratory Objectives & Endpoints

- 2.3.1** Intratumoral Assessment:
Fresh biopsy or archived tissue will be used if available. PD-L1 protein on tumor cells and the expression levels of other markers of inflammatory/immune signature that may include but not be limited to PD-1, OX40, CD73, CD39, T cell immunoglobulin and TIM3, GITRL, CTLA-4, CD3, CD4, CD8, CD45RO, FOXP3, and granzyme by IHC and/or flow cytometry will be evaluated. Whole exome sequencing and computational analyses will be performed to assess mutanome and immunome (subpopulations of immune cells).
- 2.3.2** Circulating free DNA (cfDNA) mutation analyses:
Blood will be drawn before treatment and every 8 weeks with imaging for the first 24 weeks then every 16 weeks until disease progression. Change in clonal burden landscape of various mutanome and immunome will be analyzed to investigate its correlation with treatment response or development of resistance to treatment.

3.0 PATIENT ELIGIBILITY

The target population for this study is patients with hepatocellular carcinoma. This will be a single-center trial conducted at Robert H. Lurie Comprehensive Cancer Center (RHLCCC) of Northwestern University.

Up to 40 patients will be enrolled, up to 15 in Phase 1 and up to an additional 25 in Phase 1b. Approximately 3 potentially eligible patients are seen per month, and it is anticipated that at least 2 per month will be accrued. Potential patients may be referred to the Principal Investigator (PI) at Northwestern University, [name], at [contact]

Eligibility will be evaluated by the study team according to the following criteria. Eligibility waivers are not permitted. Subjects must meet all of the inclusion and none of the exclusion criteria to be registered to the study. Study treatment may not begin until a subject is registered. Please refer to Section 11.4 for complete instructions regarding registration procedures.

3.1 Inclusion Criteria

- 3.1.1** Patients must have a diagnosis of hepatocellular carcinoma (HCC) confirmed by American Association for Study of Liver Diseases (AASLD) guidelines with a Childs-Pugh score of A or B (but, \leq Childs score B8).
NOTE: If the patient does not have histological confirmation of disease by biopsy, diagnosis of HCC must be documented with approval by a tumor board or other multidisciplinary conference. Please refer to the appropriate source document in NOTIS.
- 3.1.2** Patients must have at least 1 lesion that is measurable using RECIST guidelines.
NOTE: A previously irradiated lesion can be considered a target lesion if the lesion is well defined, measurable per RECIST, and has clearly progressed.
NOTE: For patients with infiltrative disease, evaluable disease needs to be confirmed by pathology if RECIST measurements cannot be made.
- 3.1.3** Patients must have advanced disease that is not amenable to transplant or resection.
- 3.1.4** Patients may be treatment naïve or have received any number of prior therapies.
NOTE: Prior immunotherapy is contraindicated and not permitted.
- 3.1.5** Patients with chronic Hepatitis B are eligible as long as they have evidence of ongoing viral replication (detectable HBsAg, HBeAg, or HBV DNA). They must have HBV DNA viral load <100 IU/mL at screening. In addition, they must be on antiviral therapy per regional standard of care guidelines prior to initiation of study therapy. If not on antiviral therapy at screening, then the subject must initiate treatment per regional standard of care guidelines at the time of consent. Both HBeAg positive and negative patients will be included.
- 3.1.6** Patients positive for Hepatitis C are permitted if controlled with medication, in the opinion of the investigator.
- 3.1.7** Adults ≥ 18 years old of either gender are eligible.
- 3.1.8** Patients must exhibit an ECOG performance status of 0, 1, or 2.

- 3.1.9** Patients must have adequate organ function within 14 days prior to registration as determined by:
- Hematological (without growth factor support)
 - Hemoglobin \geq 8.5 g/dL (without the use of growth factors)
 - ANC \geq 1000
 - Platelet count \geq 50 x 10⁹/L (without use of growth factors [i.e., IL-11 {Oprevekin}])
 - Prothrombin time (PT)/ International normalized ratio (INR) \leq 2.3 or PT \leq 6 seconds above control.
NOTE: Abnormal PT/INR may be considered, with documented PI approval, if it is due to the use of anticoagulants. For such patients, a normal PT/INR must be available from before the start of anticoagulation treatment.
NOTE: Performed at time of screening angiogram; can be outside 14 days if applicable.
 - Renal
 - Calculated creatinine clearance* (CrCl) or 24-hour urine CrCl > 30 mL/min (*Cockcroft-Gault formula will be used to calculate CrCl)
 - Hepatic
 - Serum Bilirubin \leq 3 times the upper limit of normal (ULN)
 - AST and ALT \leq 5 times ULN
 - Serum Electrolytes
 - Potassium, sodium, and calcium (corrected for serum albumin) \leq Grade 1 or within the institutional ranges of normal. If clinically appropriate, electrolytes may be corrected and values re-assessed prior to enrollment
- 3.1.10** Females of childbearing potential (FOCBP), and non-sterilized males who are sexually active must agree to the use of two methods of contraception, with one method being highly effective and the other method being either highly effective or less effective as listed in Appendix 2. They must also refrain from egg and/or sperm cell donation and breastfeeding for 90 days after the final dose of investigational product(s)
- Females of childbearing potential are defined as those who are not surgically sterile (i.e., bilateral tubal ligation, bilateral oophorectomy, or complete hysterectomy) or postmenopausal (defined as 12 months with no menses without an alternative medical cause)
 - WOCBP must agree to follow instructions for method(s) of contraception for the duration of treatment with nivolumab plus 5 half-lives of nivolumab (19 weeks) plus 30 days (duration of ovulatory cycle) for a total of 23 weeks post-treatment completion.
 - Men who are sexually active with WOCBP must agree to follow instructions for method(s) of contraception for the duration of treatment with nivolumab plus 5 half-lives of the study drug (19 weeks) plus 90 days (duration of sperm turnover) for a total of 31 weeks post-treatment completion
- 3.1.11** FOCBP must have a negative pregnancy test within 7 days prior to registration
Note: FOCBP will have to have repeat pregnancy test within 24 hours of starting nivolumab, scheduled for Cycle 1 Day 1.
- 3.1.12** Subjects must provide archived tumor specimens for correlative biomarker studies if sufficient tissue is available. A fresh biopsy is not required.

3.1.13 Patients must have the ability to understand and the willingness to sign a written informed consent prior to registration on study.

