APPENDIX 2:

Pregnancy and Contraception Requirements

Investigators shall counsel WOCBP and male subjects who are sexually active with WOCBP on the importance of pregnancy prevention and the implications of an unexpected pregnancy. Investigators shall advise WOCBP and male subjects who are sexually active with WOCBP on the use of highly effective methods of contraception from the time of treatment initiation to 5 months (for FOCBP) or 7 months (for males with FOCBP partners) after the last dose of nivolumab. Highly effective methods of contraception have a failure rate of < 1% per year when used consistently and correctly.

At a minimum, subjects must agree to the use of two methods of contraception, with one method being highly effective and the other method being either highly effective or less effective as listed below:

HIGHLY EFFECTIVE METHODS OF CONTRACEPTION

Male condoms with spermicide

- a) Hormonal methods of contraception including combined oral contraceptive pills, vaginal ring, injectables, implants, and intrauterine devices (IUDs) such as Mirena® by WOCBP subject or male subject's WOCBP partner. Female partners of male subjects participating in the study may use hormone based contraceptives as one of the acceptable methods of contraception since they will not be receiving study drug.
- b) Nonhormonal IUDs, such as ParaGard®
- c) Tubal ligation
- d) Vasectomy.
- e) Complete Abstinence*

*Complete abstinence is defined as complete avoidance of heterosexual intercourse and is an acceptable form of contraception for all study drugs. Subjects who choose complete abstinence are not required to use a second method of contraception, but female subjects must continue to have pregnancy tests. Acceptable alternate methods of highly effective contraception must be discussed in the event that the subject chooses to forego complete abstinence.

LESS EFFECTIVE METHODS OF CONTRACEPTION

- a) Diaphragm with spermicide
- b) Cervical cap with spermicide
- c) Vaginal sponge
- d) Male Condom without spermicide*
- e) Progestin only pills by WOCBP subject or male subject's WOCBP partner
- f) Female Condom*

*A male and female condom must not be used together

[figure not shown]
Azoospermic males and WOCBP who are continuously not heterosexually active are exempt from contraceptive requirements. However they must still undergo pregnancy testing as described in this section.

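### Section 3.1.10 states the male contraception period as 31 weeks although its parts sum to 31.9, and Appendix 2 gives shorter periods for both sexes

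*Combined protocol and SAP*

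**What the plan says.** Three rules in current text bear on this point.

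- **Section 3.1.10, contraception.** Women of childbearing potential agree to contraception during nivolumab treatment "plus 5 half-lives of nivolumab (19 weeks) plus 30 days (duration of ovulatory cycle) for a total of 23 weeks post-treatment completion". Men with such partners agree to it during treatment "plus 5 half-lives of the study drug (19 weeks) plus 90 days (duration of sperm turnover) for a total of 31 weeks post-treatment completion".
- **Appendix 2, contraception.** Investigators are to advise highly effective contraception from the start of treatment "to 5 months (for FOCBP) or 7 months (for males with FOCBP partners) after the last dose of nivolumab". Section 3.1.10 sends the reader to this appendix for the list of methods.
- **Section 3.1.10, donation and breastfeeding.** The same criterion has participants "refrain from egg and/or sperm cell donation and breastfeeding for 90 days after the final dose of investigational product(s").

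Section 3.0 requires every inclusion criterion to be met and allows no waivers. No section says whether 3.1.10 or Appendix 2 governs the duration.

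**The concern.** A period built from named parts should equal the sum of those parts, and two sections that set the same safety period should give the same end date. Neither holds here for men, and the second does not hold for women.

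What is at stake is a reproductive-safety rule inside an eligibility criterion. Section 3.1.10 fixes what the participant agrees to, and Appendix 2 fixes what the investigator advises. A site that works from the appendix would name an earlier end date than the one agreed at entry.

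The donation rule raises a related question. Its 90 days end before the 19 weeks that the same criterion counts as drug wash-out.

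**Working it through.** **Inputs.** From 3.1.10: five half-lives = 19 weeks = 19 × 7 = 133 days; added period 90 days (men) or 30 days (women); stated totals 31 weeks (men) and 23 weeks (women); donation bar 90 days. From Appendix 2: 7 months (men) and 5 months (women). I count every period from the last nivolumab dose, and months by calendar, over all possible starting months.

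**Step 1: the stated totals.**

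- Women: 133 + 30 = 163 days; 163 / 7 = 23.29 weeks. To the nearest week this is 23, so the plan's figure reproduces (23 weeks = 161 days).
- Men: 133 + 90 = 223 days; 223 / 7 = 31.86 weeks. Rounding to nearest or rounding up gives 32; only dropping the fraction gives 31. The plan's 31 weeks is 217 days, and 223 − 217 = 6 days.

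**Step 2: could rounding of the 19 weeks explain the 31?** For the male sum to round to 31, the unrounded five half-lives must be below 31.5 − 90/7 = 18.64 weeks, a half-life below 18.64 × 7 / 5 = 26.1 days. The printed 19 weeks implies 133 / 5 = 26.6 days. The documents give no separate half-life, so this explanation is possible but has no support in them.

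**Step 3: Appendix 2 against 3.1.10.**

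| | Sum of parts in 3.1.10 | Stated in 3.1.10 | Appendix 2 |
|---|---|---|---|
| Men | 223 days (31.9 weeks) | 217 days (31 weeks) | 7 months = 212–215 days (30.3–30.7 weeks) |
| Women | 163 days (23.3 weeks) | 161 days (23 weeks) | 5 months = 150–153 days (21.4–21.9 weeks) |

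Appendix 2 falls short as follows:

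- Men: 217 − 215 = 2 to 217 − 212 = 5 days against the stated total; 223 − 215 = 8 to 223 − 212 = 11 days against the sum.
- Women: 161 − 153 = 8 to 161 − 150 = 11 days against the stated total; 163 − 153 = 10 to 163 − 150 = 13 days against the sum.

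**Step 4: the donation bar.** It ends at 90 days (90 / 7 = 12.9 weeks). The wash-out counted in the same criterion ends at 133 days, which is 133 − 90 = 43 days later. A man's stated contraception period runs to day 217, so for 217 − 90 = 127 days he would have to use contraception without being barred from donating sperm.

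**The case against.** The best defence is that these are rounding effects of a few days. Dropping fractions of a week yields both printed totals, 31 and 23. At 30.44 days per month, 223 days is 7.3 months and 163 days is 5.4 months, which round to the 7 and 5 of Appendix 2. The two rules are also nested: a participant who keeps to the 23 or 31 weeks of 3.1.10 has already satisfied Appendix 2.

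Most of this stands, and it limits the size of the point. It does not remove it. In a minimum period, dropping the fraction ends the period before its own components do. The nesting works in one direction only: a participant advised by Appendix 2 can stop before the period agreed under 3.1.10.

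Three stronger readings are tempting, and the documents do not support them.

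- **That both totals are miscalculated.** Only the male one is; the female one is correct to the nearest week.
- **That patients are being told conflicting things.** The consent pages are not among the material available for review, so what patients are told cannot be checked. The documents show only that the protocol text gives different durations.
- **That the 90-day donation bar is an error in the contraception period, or is too short.** It is a separate restriction, and no section requires it to equal the contraception period. Whether it is long enough is a clinical question. The text supports only the observation that it sits uneasily with the 19-week wash-out in the same criterion.

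**Conclusion.** The point holds as a small inconsistency in a safety rule. The male total in 3.1.10 is 6 days less than the sum of its parts. Appendix 2 is shorter than the stated totals by 2–5 days for men and 8–11 days for women, and nothing says which section governs. The donation bar ends 43 days before the wash-out that the same criterion counts, and rounding cannot account for that gap; whether it is intended is for the sponsor to say.

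The figures assume that 19 weeks means exactly 133 days, that all periods start at the last nivolumab dose, and that months are calendar months. The dose-escalation rules, the Simon design, the endpoints and the analyses are untouched. The reason to act is clarity of a non-waivable safety criterion. This review takes no position on which duration is right.

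**What to change.** - Reconcile 3.1.10 and Appendix 2 to one period per sex, expressed in one unit and in agreement with the components from which it is built.
- Have the sponsor confirm that the 90-day donation period is intended alongside the stated 19-week wash-out, or reconcile the two.
- Check that the patient information carries the same periods.

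The sponsor decides the durations. The cost is wording in two places of the protocol and, if it differs, the matching patient information. No recalculation of the design is needed.

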3.2 Exclusion Criteria

3.2.1 Patients must not have had prior treatment with nivolumab or any other PDL1 or PD-1 antagonists

3.2.2 Patients must not have a history of severe allergic reactions (i.e., Grade 4 allergy, anaphylactic reaction from which the subject did not recover within 6 hours of institution of supportive care) to any unknown allergens or any components of the nivolumab formulations

3.2.3 Patients diagnosed or treated for malignancy other than HCC are not eligible unless they meet one of the following exceptions:

- Malignancy treated with curative intent and with no known active disease present for ≥ 3 years before registration and felt to be at low risk for recurrence by the treating physician.
- Adequately treated non-melanoma skin cancer or lentigo maligna without evidence of disease.
- Adequately treated cervical carcinoma in situ without evidence of disease

3.2.4 Patients with active autoimmune disease or history of autoimmune disease that might recur, which may affect vital organ function or require immune suppressive treatment including chronic prolonged systemic corticosteroids (defined as corticosteroid use of duration one month or greater), should be excluded. These include but are not limited to patients with a history of:

- immune related neurologic disease
- multiple sclerosis
- autoimmune (demyelinating) neuropathy
- Guillain-Barre syndrome
- myasthenia gravis
- systemic autoimmune disease such as SLE
- connective tissue diseases
- scleroderma
- inflammatory bowel disease (IBD)
- Crohn's
- ulcerative colitis
- patients with a history of toxic epidermal necrolysis (TEN)
- Stevens-Johnson syndrome
- anti-phospholipid syndrome

NOTE: Subjects with vitiligo, type I diabetes mellitus, residual hypothyroidism due to autoimmune condition only requiring hormone replacement, psoriasis not requiring systemic treatment, or conditions not expected to recur in the absence of an external trigger are permitted to enroll.

3.2.5 Patients with renal failure currently requiring dialysis of any kind are not eligible.

3.2.6 Patients with untreated central nervous system (CNS) metastatic disease (including spinal cord and leptomeningeal disease) are excluded.
Note: Subjects with previously treated CNS metastases that are radiographically and neurologically stable for at least 6 weeks and do not require corticosteroids (of any dose) for symptomatic management are permitted to enroll

NU Study Number: NU 16101
BMS Study Number: CA 209-615

- 3.2.7** Concurrent enrollment in another clinical study, unless it is an observational (non-interventional) clinical study or the follow-up period of an interventional study, is excluded.
- 3.2.8** Receipt of any investigational therapy is not permitted within 28 days prior to the first dose of nivolumab
- 3.2.9** Any concurrent chemotherapy, biologic or hormonal therapy for cancer treatment is not permitted within 28 days of registration.
Note: Prior immunotherapy is not permitted.
Note: Concurrent use of hormones for non-cancer-related conditions (e.g., insulin for diabetes and hormone replacement therapy) is acceptable.
- 3.2.10** Patients with exposure to prior immunotherapy are not eligible.
- 3.2.11** Patients are ineligible if they have unresolved toxicities from prior anticancer therapy, defined as having not resolved to NCI CTCAE v4.03 Grade 0 or 1 with the exception of alopecia and laboratory values listed per the inclusion criteria.
Note: Subjects with irreversible toxicity that is not reasonably expected to be exacerbated by any of the investigational products may be included (e.g., hearing loss) after consultation with the PI and NU QAM.
- 3.2.12** Radiation therapy is not permitted within 14 days of registration.
- 3.2.13** Live vaccines are not permitted within 28 days of study registration.
- 3.2.14** No systemic glucocorticoids will be permitted within 48 hours prior to study registration.
Note: Topical steroids, bronchodilators and local steroid injections are permitted if clinically required.
- 3.2.15** Patients with cardiac disease defined as one of the following are not eligible:
- Congestive heart failure > class II NYHA.
 - Unstable angina (anginal symptoms at rest) or new onset angina (began within the last 3 months)
 - Myocardial infarction within the past 6 months.
- 3.2.16** Patients with cardiac ventricular arrhythmias requiring anti-arrhythmic therapy are not eligible.
- 3.2.17** Patients with known human immunodeficiency virus (HIV) infection are not eligible.
- 3.2.18** Patients must not have elevated lung shunting precluding treatment with Y-90.
- 3.2.19** Patients who have had major surgery within 4 weeks prior to registration are not eligible.
- 3.2.20** Patients who have active clinically serious infection > CTCAE Grade 2 are not eligible.
- 3.2.21** Patients with a history of gastrointestinal bleeding (GIB) within 6 weeks prior to registration are not eligible.
- 3.2.22** Patients with prior transplant of any kind are not eligible.

3.2.23 Patients may not be pregnant or lactating at study registration.

3.2.24 Patients who have an uncontrolled intercurrent illness including, but not limited to any of the following, are not eligible:

- Hypertension that is not controlled on medication
- Ongoing or active infection requiring systemic treatment
- Psychiatric illness/social situations that would limit compliance with study requirements
- Any other illness or condition that the treating investigator feels would interfere with study compliance or would compromise the patient's safety or study endpoints
- Active alcohol use, drug use, or a psychiatric disease that would, in the opinion of the PI or a subinvestigator (sub-I), prevent the subject from complying with the study protocol and/or endanger the subject during their participation in the study

